5.1.6 Visit 5 (Lens 2: Day 30 Follow-up/Exit) – [REDACTED]

1	Obtain information on any changes in medical health and/or the use of concomitant medications.
2	Record any device deficiencies or AEs including those associated with changes in concomitant medication dosing, which are observed or reported since the previous visit.
[REDACTED]	[REDACTED]
[REDACTED]	[REDACTED]
5	Evaluate the study lenses (Lens 2) by performing: 
VA with study lenses (logMAR OD and OS, at distance)
[REDACTED]	[REDACTED] 
[REDACTED][REDACTED][REDACTED][REDACTED]
[REDACTED]	[REDACTED] [REDACTED]
[REDACTED]	[REDACTED]

9	Perform slit-lamp biomicroscopy (without contact lenses) [REDACTED] [REDACTED] [REDACTED] [REDACTED] [REDACTED] [REDACTED] [REDACTED] [REDACTED] [REDACTED] [REDACTED] [REDACTED] [REDACTED]
10	If warranted, perform Manifest Refraction and BCVA with manifest refraction (OD, OS, Snellen distance).
11	Perform VA with habitual correction (OD, OS, Snellen distance). [REDACTED] [REDACTED] [REDACTED] [REDACTED]
12	Assess and record any AEs and device deficiencies reported or observed during the study visit. [REDACTED] [REDACTED]
13	Exit the subject from the Part A of the study.

5.1.7 Unscheduled Visit

1	Obtain information on any changes in medical health and/or the use of concomitant medications.
2	Record any device deficiencies or AEs including those associated with changes in concomitant medication dosing, which are observed or reported since the previous visit(s). Collect any ADE/AE/Device Deficiency lenses [REDACTED]

3	Perform slit-lamp biomicroscopy (without contact lenses) [REDACTED]: 
[REDACTED][REDACTED][REDACTED][REDACTED][REDACTED][REDACTED][REDACTED][REDACTED][REDACTED][REDACTED][REDACTED][REDACTED][REDACTED]
[REDACTED]	[REDACTED]
[REDACTED]	[REDACTED]
5	Perform VA with habitual correction (OD, OS, Snellen distance).
6	Evaluate the study lenses by performing: 
• VA with study lenses (logMAR OD and OS, at distance)
7	If applicable, perform manifest refraction and BCVA distance with manifest refraction (OD, OS, Snellen)
[REDACTED]	[REDACTED]
[REDACTED]	[REDACTED]
[REDACTED]	[REDACTED] 
[REDACTED][REDACTED][REDACTED] [REDACTED] [REDACTED]
[REDACTED]	[REDACTED]
12	Assess and record any AEs and device deficiencies reported or observed during the study visit. [REDACTED] [REDACTED]
[REDACTED]	[REDACTED] [REDACTED] [REDACTED] [REDACTED]

8	
Perform slit-lamp biomicroscopy (without contact lenses) [REDACTED]
 
■ [REDACTED]■ [REDACTED]
9	
Review inclusion/exclusion criteria to determine if the subject qualifies to be in the study. If subject qualifies, record lens power to be dispensed. [REDACTED]
 
[REDACTED]
 
[REDACTED]

10	
Have the subject insert Lens 1, being careful to maintain the correct OD and OS lens assignments.
 
[REDACTED]
 
■ [REDACTED]■ [REDACTED]
11	
Evaluate the study lenses by performing:
 
• VA with study lenses (logMAR OD and OS, at distance) 
[REDACTED]
 
[REDACTED]

■	
[REDACTED]
 
■ [REDACTED]■ [REDACTED] 
[REDACTED]
 
[REDACTED]

13	
Assess and record any AEs and device deficiencies reported or observed during the study visit.
 
[REDACTED]
 
[REDACTED]

14	
Dispense study lens case and lens care solutions (CLEAR CARE contact lens solution).
 
[REDACTED]
 
 ■ [REDACTED] ■ [REDACTED]
15	
Schedule Visit 2 to take place 15 [REDACTED] days after Visit 1.
 
[REDACTED]
 
 ■ [REDACTED] ■ [REDACTED] ■ [REDACTED] ■ [REDACTED] ■ [REDACTED] ■ [REDACTED]
■	
[REDACTED]
 
[REDACTED]
 
[REDACTED]
 
[REDACTED]

5.2.3 Visit 2 (Lens 1: Day 15 Follow-up) – [REDACTED]

1	
Obtain information on any changes in medical health and/or the use of concomitant medications.

2	
Record any device deficiencies or AEs, including those associated with changes in concomitant medication dosing, which are observed or reported since the previous visit. Collect any ADE/AE/Device Deficiency lenses [REDACTED]

■	
[REDACTED]

■	
[REDACTED]

5	
Evaluate the study lenses by performing: VA with study lenses (logMAR OD and OS, at distance)

6	
[REDACTED]
 
[REDACTED][REDACTED] 
[REDACTED]
 
[REDACTED]

7	
[REDACTED]
 
[REDACTED]
 
[REDACTED]
 
[REDACTED]

8	Perform slit-lamp biomicroscopy
9	If warranted, perform Manifest Refraction and BCVA with manifest refraction (OD, OS, Snellen distance)
10	Assess and record any AEs and device deficiencies reported or observed during the study visit.
	
[REDACTED]
 
[REDACTED]

11	
[REDACTED]
 
[REDACTED] 
[REDACTED]

12	Schedule Visit 3 to take place 15 [REDACTED] days after Visit 2.
	
[REDACTED]
 
[REDACTED][REDACTED][REDACTED][REDACTED][REDACTED] 
[REDACTED]

13	
[REDACTED]
 
[REDACTED]
 
[REDACTED]
 
[REDACTED]

11	
Assess and record any AEs and device deficiencies reported or observed during the study visit.
 
 ■ [REDACTED] ■ [REDACTED] ■ [REDACTED]
12	Exit the subject from Part B of the study.

5.2.5 Unscheduled Visit

1	Obtain information on any changes in medical health and/or the use of concomitant medications.
2	Record any device deficiencies or AEs including those associated with changes in concomitant medication dosing, which are observed or reported since the previous visit(s). Collect any ADE/AE/Device Deficiency lenses [REDACTED]
3	
Perform slit-lamp biomicroscopy (without contact lenses) [REDACTED]:
 
 ■ [REDACTED]
The following are to be performed if applicable in the view of the Investigator	
■	[REDACTED]
5	Perform VA with habitual correction (OD, OS, Snellen distance).
6	
Evaluate the study lenses by performing:
 
 • VA with study lenses (logMAR OD and OS, at distance)
7	If applicable, perform manifest refraction and BCVA distance with manifest refraction (OD, OS, Snellen)
■	[REDACTED]

■	[REDACTED]
■	[REDACTED]
11	Assess and record any AEs and device deficiencies reported or observed during the study visit. [REDACTED]
■	[REDACTED]

5.3 Unscheduled Visits

Any visit that occurs between regularly scheduled visits is an Unscheduled Visit. If [REDACTED]
[REDACTED]
[REDACTED]

[REDACTED] During all unscheduled visits, the Investigator must conduct the following procedures:

- Collect AE and Device Deficiency information
- Assess and record changes in medical condition or concomitant medication
- Assess and record VAs
- Perform biomicroscopy (assessments with or without lenses, as possible)

In addition, all procedures for Visit 5 (Follow-up/Exit) should be completed (as possible). The Investigator may perform additional procedures for proper diagnosis and treatment of the subject. The Investigator must document this information in the subject's case history source documents.

If during an Unscheduled Visit the subject is discontinuing the study lenses or discontinuing from the study, the Investigator must conduct Exit procedures according to Table 1-1: Schedule of Study Procedures and Assessments, as possible.

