Associated Materials	
• CLEAR CARE® contact lens solution 
■ [REDACTED]
 
[REDACTED]
 
[REDACTED]
 
[REDACTED]
 
[REDACTED]

Table 1-1 Schedule of Study Procedures and Assessments – Part A

Procedure/ Assessment	PRESCREENING	LENS 1				LENS 2		USV
		Visit 1 Screen/ Baseline/ Dispense Lens 1	Visit 2 Day 15 Follow- up Lens 1	Visit 3 Day 30 Follow-up Lens 1 Dispense Lens 2		Visit 4 Day 15 Follow- up Lens 2	Visit 5 Day 30 Follow- up Lens 2 /Exit^	
				Follow-up Lens 1	Dispense Lens 2			
Informed Consent		X						
Demographics		X						
Medical History*		X	X	X	X	X	X	X
Concomitant Medications*		X	X	X	X	X	X	X
Inclusion/ Exclusion		X						
Habitual (lens brand, lens power*, lens care)		X						
VA w/ habitual correction* (OD, OS, Snellen distance)		X					X	(X)
Manifest Refraction and BCVA with manifest refraction* (OD, OS, Snellen distance)		X	(X)	(X)	(X)	(X)	(X)	(X)
Biomicroscopy		X	X	X		X	X	X
Randomization and record lens power*		X						
Dispense study lenses		X	(X) ^Ω		X	(X) ^Ω		(X)
VA w/ study lenses (OD, OS, logMAR distance)		X	X	X	X	X	X	(X)

Procedure/ Assessment	PRESCREENING	LENS 1			LENS 2			USV
		Visit 1 Screen/ Baseline/ Dispense Lens 1	Visit 2 Day 15 Follow- up Lens 1	Visit 3 Day 30 Follow-up Lens 1 Dispense Lens 2		Visit 4 Day 15 Follow- up Lens 2	Visit 5 Day 30 Follow- up Lens 2 /Exit^	
				Follow-up Lens 1	Dispense Lens 2			
[REDACTED]		■	■	■	■	■	■	■
[REDACTED]		■ ■	■ ■ ■	■ ■ ■	■ ■ ■	■ ■ ■	■ ■ ■	■
[REDACTED]			■	■		■	■	■
[REDACTED]		■ ■	■ ■ ■	■ ■ ■	■ ■ ■	■ ■ ■	■ ■ ■	■
[REDACTED]							■	■
[REDACTED]		■	■	■	■	■	■	■
[REDACTED]		■	■	■	■	■	■	■
AEs [§]		X	X	X	X	X	X	X
Device deficiencies		X	X	X	X	X	X	X
Exit Form		(X)	(X)	(X)	(X)	(X)	X	(X)

USV = Unscheduled visit

[REDACTED]

[REDACTED]

[REDACTED]

[REDACTED]

[REDACTED]

[REDACTED]

[REDACTED]

Table 1-2 Schedule of Study Procedures and Assessments – Part B

Procedure/ Assessment	PRESCREENING	Visit 1 Screen/ Baseline/ Dispense Lens 1	Visit 2	Visit 3 Day 30 Follow-up Lens 1/Exit^	USV
			Day 15 Follow- up Lens 1		
Informed Consent		X			
Demographics		X			
Medical History*		X	X	X	X
Concomitant Medications*		X	X	X	X
Inclusion/ Exclusion		X			
[REDACTED]		■			
Habitual (lens brand, lens power*, lens care)		X			
VA w/ habitual correction* (OD, OS, Snellen distance)		X		X	(X)
Manifest Refraction and BCVA with manifest refraction* (OD, OS, Snellen distance)		X	(X)	(X)	(X)
Biomicroscopy		X	X	X	X
[REDACTED]	■	■			
[REDACTED]		■	■	■	■
Record lens power*		X			

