5.1.3 Visit 2 (Lens 1: Day 15 Follow-up) – [REDACTED]

1	Obtain information on any changes in medical health and/or the use of concomitant medications.
2	Record any device deficiencies or AEs, including those associated with changes in concomitant medication dosing, which are observed or reported since the previous visit. Collect any ADE/AE/Device Deficiency lenses [REDACTED]
■	[REDACTED]
■	[REDACTED]
5	Evaluate the study lenses by performing: VA with study lenses (logMAR OD and OS, at distance)
6	[REDACTED] 
■ [REDACTED]■ [REDACTED] [REDACTED] [REDACTED]

■	[REDACTED]
■	[REDACTED]
9	Perform slit-lamp biomicroscopy
10	If warranted, perform Manifest Refraction and BCVA with manifest refraction (OD, OS, Snellen distance)
11	Assess and record any AEs and device deficiencies reported or observed during the study visit. [REDACTED]
■	[REDACTED]
13	Schedule Visit 3 to take place 15 [REDACTED] days after Visit 2. [REDACTED]
■	[REDACTED]

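### Do the protocol's conflicting instructions on visual acuity at unscheduled visits, and its Part A-only exit references, call for a change to the plan?

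*Protocol*

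**What the plan says.** Protocol 5.3 follows the visit sections for both Parts and, where it can be read, is not limited to either. It states "During all unscheduled visits, the Investigator must conduct the following procedures". The list covers adverse events and device deficiencies, changes in medical condition or medication, biomicroscopy, and "Assess and record VAs". The biomicroscopy item carries a qualifier; the acuity item does not.

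Protocol 5.2.5 (Part B) has a line after the biomicroscopy step: "The following are to be performed if applicable in the view of the Investigator". Step 5 (Snellen acuity with habitual correction) and step 6 (logMAR acuity with study lenses) come below it. In Protocol 5.1.7 (Part A) the same two tests appear, for example "Perform VA with habitual correction (OD, OS, Snellen distance", but the rows just before them are redacted.

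In the unscheduled-visit columns of Tables 1-1 and 1-2, both acuity rows carry a bracketed X. The footnotes that would explain the brackets are redacted.

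Section 5.3 continues: "In addition, all procedures for Visit 5 (Follow-up/Exit) should be completed (as possible". For subjects who stop the lenses or leave the study, it requires the exit procedures of Table 1-1, as far as possible.

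**The concern.** The same test at the same visit is compulsory in one section and discretionary in another, and no visible text says which prevails. A Part B site that records no acuity complies with 5.2.5 and departs from 5.3. Protocol 10.1 requires deviations to be recorded and reported, so a monitor could not tell whether this is one. Protocol 3.3 tells subjects to return promptly for symptoms that include vision changes, so sites might collect acuity unevenly just where it is informative.

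The exit wording looks like a second fault. A Part B subject has no Visit 5, and Table 1-1 is not that subject's schedule. If early leavers went without a final acuity measurement, data on the primary endpoint's measure would be lost selectively.

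**Working it through.** The plan states no figure to reproduce. The check compares the passages.

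**1. Reach of the discretionary line in 5.2.5.** Steps 5 and 6 sit below it. So does step 11, the recording of adverse events and device deficiencies, which 5.3 makes mandatory and Table 1-2 marks with a plain X at unscheduled visits. Step 7 (manifest refraction) repeats its own conditional wording, which would be redundant if the line governed everything below it. So the line either does not cover every later step or is loosely placed. No visible text ends its reach before steps 5 and 6, so the mismatch with 5.3 remains, but it is weak evidence of a deliberate rule.

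**2. The bracketed entries.** In the unscheduled-visit columns:

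| Items on the 5.3 list | Cells | Mark |
|---|---|---|
| Medical history, concomitant medications, biomicroscopy, adverse events, device deficiencies | 5 rows × 2 tables = 10 | X in 10 of 10 |
| Habitual acuity, study-lens acuity | 2 rows × 2 tables = 4 | (X) in 4 of 4 |

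Elsewhere, bracketed manifest refraction can be matched to visible step text in six places: Part A Visits 2, 4, 5 and unscheduled, and Part B Visit 2 and unscheduled. All six are conditional, as in "If warranted, perform Manifest Refraction and BCVA with manifest refraction (OD, OS, Snellen distance". But other bracketed cells depend on circumstances, not judgement. The Exit Form is bracketed before Visit 5, plausibly because a subject may leave early. Lens dispensing is bracketed at Part A Visits 2 and 4, which fits a control lens replaced every two weeks. Study-lens acuity needs a lens on the eye, and Protocol 3.3 tells symptomatic subjects to remove theirs. A bracket meaning whichever test the situation allows is compatible with 5.3, so the tally does not establish a conflict between tables and text.

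**3. Which acuity 5.3 means.** Its next sentence asks for all Visit 5 procedures as far as possible. Protocol 5.1.6 includes study-lens logMAR acuity (step 5) and habitual Snellen acuity (step 11). This is softer than the compulsory list, but it indicates both.

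**4. The exit references.** Visit 5 and Table 1-1 belong to Part A. Protocol 3.5 gives Part B three visits, and Table 1-2 labels Visit 3 as follow-up and exit, the same description that 5.3 attaches to Visit 5. Both acuity rows carry a plain X at Visit 5 in Table 1-1 and at Visit 3 in Table 1-2, so following either table yields the same two tests.

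**5. Whether any result depends on this.** Study-lens acuity has a plain X in all six scheduled columns of Table 1-1 (Visit 3 has two) and all three of Table 1-2. The primary objective compares the test lens with AOHP, the Part A control; Protocol 6 summarizes the Parts separately; the explicit discretion is visible only in Part B. Protocol 6.4.1 and SAP 4.3.1 plan descriptive statistics without hypotheses. The safety endpoints in SAP 5.1 that are visible are adverse events, biomicroscopy findings and device deficiencies, and all three are plain X at unscheduled visits.

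**The case for a change.** The strongest case for a change is that the text is contradictory and cheap to correct. The authors qualified the biomicroscopy item and not the acuity item, so the compulsory wording looks intended. If the line in 5.2.5 was never meant to cover acuity, it is misplaced and still needs moving. The redacted part of 5.3 cannot remove the visible requirement, the visible discretionary line or the visible references.

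Much of this stands: the wording is inconsistent and the references are incomplete. What does not follow is a consequence. The instructions are not mutually exclusive, since a site that records acuity satisfies both. Early leavers are covered by the separate exit requirement. SAP Section 4 does include all data from evaluable subjects and eyes, so an unscheduled value might enter a summary, but nothing visible assigns it a place there. The correction would also require a choice that only the sponsor can make, plus IRB review of an amendment under Protocol 10.2, with no identified gain in estimate, precision or safety reporting.

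**Conclusion.** The observations are accurate, but no change to the plan follows. On acuity, the text leaves a small gap that sites and monitors can fill sensibly. On exit, it contains a clerical cross-reference slip whose Part B reading is plain. The wording can be tidied if the protocol is opened for another reason; which acuity rule was meant is for the sponsor.

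The reach is limited to unscheduled visits and early exits, mainly in Part B. The documents give no rate for either, so no count is possible. No effect on the Part A comparison, the Part B summaries or the visible safety summaries can be shown.

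This rests on three assumptions: that the redacted parts of the SAP do not create a summary built on unscheduled acuity; that sites read the exit instruction as meaning their own Part's exit visit and table; and that the hidden text of 5.3, 5.1.7 and the table footnotes does not impose a stricter or different rule.

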5.4 Discontinued Subjects

Discontinued subjects are those who withdraw or are withdrawn from the study after signing the informed consent, including screen failures. Subjects may discontinue from the study at any time for any reason. Subjects may also be discontinued from the study at any time if, in the opinion of the Investigator, their continued participation poses a risk to their health.

Discontinued subjects will not be replaced [REDACTED]
[REDACTED]

[REDACTED]
[REDACTED]
[REDACTED]

[REDACTED]
[REDACTED]

[REDACTED]
[REDACTED]

[REDACTED]
[REDACTED]

[REDACTED]
[REDACTED]
[REDACTED]

5.5 Clinical Study Termination

The Study Sponsor reserves the right to close the investigational site or terminate the study in its entirety at any time, for reasonable cause.

[REDACTED]

- [REDACTED]
 - [REDACTED]
[REDACTED]
 - [REDACTED]
[REDACTED]
[REDACTED]
- [REDACTED]

- [REDACTED]
- [REDACTED]

[REDACTED]

■ [REDACTED]

[REDACTED]

6 ANALYSIS PLAN

Part A and Part B will be summarized and presented separately.

Continuous variables will be summarized using the number of observations, mean, standard deviation, median, minimum, and maximum. Categorical variables will be summarized with counts and percentages from each category.

Any deviations to this analysis plan will be updated during the course of the study as part of a protocol amendment or will be detailed in the clinical study report.

6.1 Subject Evaluability

The final subject evaluability for Part A will be determined prior to breaking the code for masked treatment (lens) sequence assignment and locking the respective subject data, based on the Deviations and Evaluability Plan (DEP).

Similarly, final subject evaluability for Part B will be determined prior to locking the database, based on the DEP.

6.2 Analysis Data Sets

6.2.1 Safety Analysis Set

Safety analyses will be conducted using the safety analysis set on a treatment-emergent basis. As such, the safety analysis set will include all subjects/eyes exposed to any study lenses evaluated in this study. For treatment-emergent safety analyses, subjects/eyes will be categorized under the actual study lenses exposed.

6.3 Demographic and Baseline Characteristics

Demographic information (age, sex, ethnicity, race) will be summarized on the Safety Analysis Set. Baseline data pertaining to habitual lens (lens brand, lens care brand) [REDACTED] will be summarized on the Safety Analysis Set as well.

6.4 Effectiveness Analyses

This study defines one primary endpoint [REDACTED]. The Safety Analysis Set will be used for all effectiveness analyses.

6.4.1 Primary Effectiveness

The primary objective of this study is to evaluate the overall performance of an investigational silicone hydrogel lens when compared to AOHP. The primary endpoint is distance VA with study lenses, collected in logMAR, for each eye.

6.4.1.1 Statistical Hypotheses

No inferences are to be made on the primary effectiveness endpoint; therefore, no hypotheses are formulated.

6.4.1.2 Analysis Methods

Descriptive statistics will be presented.

[REDACTED]

[REDACTED]

[REDACTED]

- [REDACTED]
- [REDACTED]

All AEs occurring from the time a subject signs informed consent to study exit will be accounted for in the reporting. Descriptive summaries (counts and percentages) for ocular and nonocular AEs will be presented by Medical Dictionary for Regulatory Activities Preferred Terms. AEs leading to study discontinuation, significant non-serious AEs, and SAEs will be identified. Individual subject listings will be provided, as necessary.

[REDACTED]

[REDACTED]

[REDACTED]

No inferential testing will be done for safety analysis.

[REDACTED]

6.10 Sample Size Justification

No formal sample size calculation is provided given the descriptive and pilot nature of the study.

7 ADVERSE EVENTS AND DEVICE DEFICIENCIES

Terms and Definitions

Adverse Event (AE)	Any untoward medical occurrence, unintended disease or injury, or untoward clinical signs (including abnormal laboratory findings) in subjects, users or other persons, whether or not related to the investigational medical device (test product). Note: For subjects, this definition includes events related to the test product, the control product, or the procedures involved. For users or other
--------------------	--

	persons, this definition is restricted to events related to the test product.
Adverse Device Effect (ADE)	AE related to the use of an investigational medical device (test product) or control product. Note: This definition includes AEs resulting from insufficient or inadequate instructions for use, deployment, implantation, installation, or operation; any malfunction; and use error or intentional misuse of the test product or control product.
Anticipated Serious Adverse Device Effect	Serious ADE which by its nature, incidence, severity or outcome has been identified in the risk management file.
Device Deficiency	Inadequacy of a medical device with respect to its identity, quality, durability, reliability, safety, or performance. Note: This definition includes malfunctions, use errors, and inadequate labeling.
Malfunction	Failure of a medical device to meet its performance specifications or otherwise perform as intended. Performance specifications include all claims made in the labeling of the device. The intended performance of the device refers to the intended use for which the device is labeled or marketed.
Non-serious Adverse Event	AE that does not meet the criteria for an SAE.
Serious Adverse Event (SAE)	
AE that led to any of the following:
 
 • Death. • A serious deterioration in the health of the subject that either resulted in: 
 a) a life-threatening illness or injury. Note: Life-threatening means that the individual was at immediate risk of death from the event as it occurred, ie, it does not include an event which hypothetically might have caused death had it occurred in a more severe form. b) any potentially sight-threatening event or permanent impairment to a body structure or a body function. c) in-patient hospitalization or prolonged hospitalization. Note: Planned hospitalization for a pre-existing condition, without serious deterioration in health, is not considered an SAE. In general, hospitalization signifies that the individual remained at the hospital or emergency ward for

	
observation and/or treatment (usually involving an overnight stay) that would not have been appropriate in the physician's office or an out-patient setting. Complications that occur during hospitalization are adverse events. If a complication prolongs hospitalization or fulfills any other serious criteria, the event is serious. When in doubt as to whether "hospitalization" occurred, the event should be considered serious.
 
d) a medical or surgical intervention to prevent a) or b).
 
e) any indirect harm as a consequence of incorrect diagnostic test results when used within manufacturer's instructions for use.
 
 • Fetal distress, fetal death, or a congenital abnormality or birth defect. 
Refer to Section 7.1 for additional SAEs.

Serious Adverse Device Effect (SADE)	ADE that has resulted in any of the consequences characteristic of an SAE.
Significant Non-Serious Adverse Event	A significant non-serious AE is a symptomatic, device-related, non-sight threatening AE that warrants discontinuation of any contact lens wear for greater than or equal to 2 weeks. Refer to Section 7.1 for additional Significant Non-Serious AEs.
Unanticipated Serious Adverse Device Effect	Serious adverse device effect which by its nature, incidence, severity or outcome has not been identified in the risk management file.
Use Error	Act or omission of an act that results in a different medical device response than intended by manufacturer or expected by user. Note: This definition includes slips, lapses, and mistakes. An unexpected physiological response of the subject does not in itself constitute a use error.

